4.1 Overall Design

This is a collaborative multi-center 2-arm clinical trial comparing: a) transvaginal sacrospinous rectopexy (TSR) with and without conventional vaginal prolapse surgery (CVPS); vs. b) laparoscopic abdominal ventral rectopexy (LAVR) with and without conventional vaginal prolapse surgery (CVPS) for ODS. A standardized common protocol for enrollment, treatment and data collection will be employed by the Clinical Sites and coordinated by the Data Coordinating Center (DCC). Women with and without vaginal prolapse who report OD symptoms in more than 50% of their bowel movements with significant rectal hypermobility (more than 50% compression ratio in dynamic posterior compartment ultrasound) will be approached for eligibility, consent, and enrollment. Participants who meet eligibility criteria and have provided informed consent will be randomly assigned to either abdominal or transvaginal rectopexy procedure (12, 62-64). Prior to randomization, eligible participants will undergo chart review by the anesthesiologist to ensure medical eligibility for both procedures.

Participants will receive the allocated transvaginal sacrospinous rectopexy surgery along with or without CVPS or laparoscopic abdominal ventral rectopexy surgery with or without CVPS as indicated for each individual and as determined before surgery (exceptions are allowed during the surgery if the surgeon decides that changing the surgical plan is in the best interest of the patient; this will be recorded as a protocol deviation). CVPS includes vaginal prolapse repair surgeries (anterior vaginal repair, posterior repair, and vault suspension) and abdominal prolapse repair surgery (sacrocolpopexy). If the participants report stress urinary incontinence at baseline, they will also receive a Tension-Free Vaginal Tape (Advantage FitTM, Boston Scientific). The primary objective of the surgical intervention is to compare the surgical success of rectal hypermobility surgery using TSR to surgery using LAVR 24 months postoperatively. The secondary objectives include comparing the change in pelvic floor disorder symptoms including OD and fecal incontinence symptoms, QOL and the incidence of perioperative and postoperative complications of these two rectal suspension procedures. We will also describe the motivations and barriers for individual women's participation in women's health research at 24 months after surgery in all participants. Data collection will occur at baseline, surgery and during hospitalization, and at 2 weeks, and 2-, 12-, and 24-months postoperatively.

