 3. Global improvement in bladder function – Participants will complete the Patient Global Impression of Improvement (69) at 2, 12 and 24 months postoperatively.
 4. Pelvic Floor Distress Inventory (PFDI) – Prolapse and colorectal symptoms as assessed by the Pelvic Organ Prolapse Distress Inventory (POPDI) and Colorectal Anal Distress Inventory (CRADI) (short-term) and urinary and colorectal symptoms as assessed by the Urinary Distress Inventory (UDI) and CRADI (long-term) subscales at 2, 12, and 24 months postoperatively.
 5. Quality of life measured by Pelvic Floor Impact Questionnaire (PFIQ) (65), Short Form Health Survey (SF-36) (70), EuroQol-5D (EQ-5D) (71) at 2, 12 and 24 months postoperatively. The SF-36 will also be administered to a subset of participants 2 weeks post-operatively to allow validation of the Pain and Activity Assessment Scale.

6. Pelvic muscle strength measured by the Brink Scale at 2, 12, and 24 months postoperatively (72).

- Compare the use of posterior compartment dynamic pelvic ultrasound imaging versus MR defecography to measure occult rectal hypermobility.
- Develop and validate a computational finite element model and statistical shape modeling approach to describe the mechanics of normal defecation and the role of rectal and vaginal support deficiencies in causing OD symptoms.

4. Study Design

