8.1 Study Assessments

The surgical success or failure of will be measured by:

1. The degree of rectal hypermobility measured via dynamic pelvic ultrasound (i.e. compression ratio)

The criteria for surgical failure will be defined as follows:

1. A participant will be considered a surgical failure if:
 - b. Rectal hypermobility with compression ratio more than 20% is detected via ultrasound.
2. Otherwise, a participant will be considered a surgical "success".

In addition to dynamic pelvic ultrasound, the following assessments will be performed:

1. Postoperative pain - Participants will complete the Pain Scale (67) and an assessment of pain medication use preoperatively, and then at 2 weeks, 2, 12 and 24 months postoperatively.
2. Postoperative functional activity level – Participants will complete the Activity Assessment Scale (68) which measures functional activity preoperatively and then at 2 weeks, 2 months, 12 months, and 24 months postoperatively.
3. Global improvement in bladder function – Participants will complete the Patient Global Impression of Improvement (69) at 2, 12 and 24 months after surgery.
4. Pelvic Floor Distress Inventory (PFDI) – Prolapse and colorectal symptoms as assessed by the POPDI and CRADI (short-term) and urinary and colorectal symptoms as assessed by the UDI and CRADI (long-term) subscales. Change in symptoms from 2, 12, and 24 months will also be assessed.
5. Quality of life measured by PFIQ (65), SF-36 (70), and EQ-5D (71) at 2, 12 and 24 months. The SF-36 will also be administered to a subset of participants 2 weeks post-operatively to allow validation of the Pain and Activity Assessment Scale.
6. Pelvic muscle strength as assessed by the Brink Scale 2, 12 and 24 months.

Based on measurements above, efficacy will be defined as follows:

1. Time to anatomic recurrence (time to failure)

- a. Urinary function: compare UDI scores (65) to assess urinary function generally and Hunskaar Incontinence Severity Index to assess the presence and severity of urinary incontinence specifically. Participants will also complete the Patients Global Impression of Improvement (PGI-I) (69) for impressions of bladder function.
- b. Bowel function: compare CRADI scores (65)
- c. Prolapse symptoms: compare POPDI scores (65)

2. Non-surgical treatment for pelvic floor disorders

- a. Pessary use for prolapse
- b. Stress urinary incontinence
- c. Urge urinary incontinence and other overactive bladder symptoms
- d. Voiding dysfunction

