9.4.2 Analysis of the Primary Efficacy Endpoint(s)

Anatomical Surgical Outcome

The primary endpoint for the surgical treatment is dichotomous: success or failure at 24 months after surgery. The primary outcome measure uses the rectal compression ratio at 24 months unless there has been retreatment at an earlier time. When there is retreatment, or when the 24-month ultrasound results and POPQ results are missing and the last observed measurements were consistent with the definition of failure, then the results at 24 months will be imputed to be a failure. A sensitivity analysis will be performed to study the effect on the primary endpoint of different methods of handling dropouts and missing data. It will be conducted by assuming various values for the imputed outcomes and comparing the results under those assumptions to the results of the primary analysis.

Cochran-Mantel-Haenszel (CMH) test will be used to compare between surgical treatments adjusting for stratification factor. In addition, Generalized linear mixed-effects models (GLMMs) will be performed to yield an effect estimate of conditional on surgeon. Demographics and other characteristics at baseline (treatment group, age, BMI, menopausal status, parity, duration and severity of ODS) will be included. Surgeon will be included as a random effect to account for

correlation between outcomes of patients treated by the same surgeon. Adjusted odds ratios (ORs) will be presented with 95% confidence intervals (CIs).

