Brink assessment will be completed by investigators during 2-month, 12-month, and 24-month post-operative appointments. Participants will be asked to be in the dorsal lithotomy position. The Brink assessment will be performed by placing 1 or 2 lubricated fingers vaginally during a single Kegel contraction. The brink scale consists of 3 separate 4-point rating scales for vaginal pressure, vertical displacement of examiner's fingers, and duration of contraction. The pressure felt by examining fingers is rated 1 ("no response"), 2 ("weak squeeze"), 3 ("moderate squeeze"), or 4 ("strong squeeze"). The vertical displacement is rated 1 ("none"), 2 ("finger base moves anteriorly"), 3 ("whole length of fingers move anteriorly"), or 4 ("whole fingers move anteriorly, are gripped and pulled in"). Duration of contraction (in seconds)

is timed and scored 1 ("none"), 2 ("<1 second"), 3 ("1–3 seconds"), or 4 (">3 seconds"). Ratings are summed to obtain total scores, with a possible range of scores of 3 to 12.

Bowel Habit

Bowel habits will be assessed by the research personnel during screening, 2-month, 12-month, and 24-month post-operative appointments. The participant will be asked about the average frequency of bowel movements in the past 3 months (more than 3 times per day, 2 to 3 times per day, once per day, 2 to 4 times per week, or less than once a week). Then the participant will be asked to identify one of the seven stool types that applies to their usual bowel movement in the past 3 months.

Pelvic Floor Distress Inventory (PFDI) Assessment

PFDI assessment will be completed by the research personnel during screening, 2-month, 12-month, and 24-month post-operative appointments. PFDI has 20 items and 3 scales of symptoms. All items use the format with a response scale from 0 (symptom is not present) to 4 (symptom is present quite a lot). The mean value of all the answered items within each scale will be multiplied by 25 to obtain the scale score (range 0 to 100). Missing items are dealt with by using the mean from answered items only. The PFDI summary score will be obtained by adding the scores from the 3 scales together (range 0 to 300).

Pain Scale and Pain Medication Use

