Pain scale and pain medication use assessment will be completed by the research personnel during screening, 2-week, 2-month, 12-month, and 24-month post-operative appointments. Participants will be asked to rate the average amount of pain within the past 24 hours while at rest, with normal activities, with exercise, and worst pain of the today. All items use the format with a response scale from 0 (no pain sensation) to 10 (most intense pain imaginable). Then the participant will be asked if they are currently taking narcotic pain medication.

Activity Scale

Activity scale will be completed by the research personnel during screening, 2-week, 2-month, 12-month, and 24-month post-operative appointments. Participants will be presented with 13 activities in which they will be asked to rate how difficult it was for them to perform them in the past 24 hours. The rating will be 1 (no difficulty), 2 (a little difficulty), 3 (some difficulty), 4 (a lot of difficulty), 5 (not able to do it), and 6 (did not do it for other reasons). Then, participants will be asked 5 additional questions regarding activity in the past month.

Impression of Improvement

Impression of improvement assessment will be completed by the research personnel during 2-month, 12-month, and 24-month post-operative appointments. Participants will be asked to indicate a number that best describes their current post-operative condition in comparison to how it was pre-operatively. The rating will be 1 (very much better), 2 (much better), 3 (a little better), 4 (no change), 5 (a little worse), 6 (much worse), and 7 (very much worse).

Pelvic Floor Impact Questionnaire (PFIQ)

PFDI assessment will be completed by research personnel during 2-month, 12-month, and 24-month post-operative appointments. The PFIQ-7 consists of 7 questions that need to be answered 3 times each considering symptoms related to the bladder or urine, vagina or pelvis, and bowel or rectum and its effect on function, social health, and mental health in the past 3 months. The responses for each question range from 0 (not at all) to 3 (quite a bit). To get scale scores, the mean of each of the 3 scales is individually calculated, which ranges from 0-3. This number is then multiplied by 100 and then divided by 3. The scale scores are then added together to get the total PFIQ-7 score, which ranges from 0-300.

Short Form (SF) - 36

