SF-36 assessment will be completed by the research personnel during 2-week, 2-month, 12-month, and 24-month post-operative appointments. SF-36 is comprised of 36 questions that cover eight domains of health: limitations in physical activities because of health problems, limitations in social activities because of physical or emotional problems, limitations in usual role activities because of physical health problems, bodily pain, general mental health (psychological distress and well-being), limitations in usual role activities because of emotional problems, vitality (energy and fatigue),

and general health perceptions. Participants will be asked to fill out the questionnaire by themselves. Then the research personnel will input the questionnaire results into an online scoring calculator (<https://orthotoolkit.com/sf-36/>).

EuroQol-5 Dimension (EQ-5D)

EQ-5D assessment will be completed by the research personnel during 2-month, 12-month, and 24-month post-operative appointments. The EQ-5D covers 5 dimensions (mobility, self-care, usual activities, pain/discomfort, and anxiety/depression), and each dimension has 5 levels: no problems, slight problems, moderate problems, severe problems, and extreme problems/unable to. There are 3,125 possible health states defined by combining one level from each dimension, ranging from 11111 (full health) to 55555 (worst health).

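### PFIQ, SF-36, EQ-5D and Brink are measured only after surgery, and the secondary models omit baseline scores even where they exist; pre-to-post change on four instruments and some precision are lost

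*Combined protocol and SAP*

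**What the plan says.** Section 4.1 lists the secondary objectives: "The secondary objectives include comparing the change in pelvic floor disorder symptoms including OD and fecal incontinence symptoms, QOL", followed by the incidence of complications. The same section counts baseline among the data collection points.

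Timing of the four instruments:

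- **PFIQ, SF-36, EQ-5D.** Section 3 measures quality of life by PFIQ, SF-36 and "EuroQol-5D (EQ-5D) (71) at 2, 12 and 24 months postoperatively", with SF-36 also at 2 weeks in a subset. Appendix D (the assessments SOP) agrees for SF-36: "SF-36 assessment will be completed by the research personnel during 2-week, 2-month, 12-month, and 24-month post-operative appointments". It gives EQ-5D the three later visits. Under the PFIQ heading it reads "PFDI assessment will be completed by research personnel during 2-month, 12-month, and 24-month post-operative appointments"; the instrument name there looks like a slip, because PFDI has its own paragraph, which includes screening.
- **Brink.** Appendix D: "Brink assessment will be completed by investigators during 2-month, 12-month, and 24-month post-operative appointments".
- **Schedules.** Section 1.3 shows post-operative visits only for all four. Appendix E does so for the three questionnaires and has no Brink entry.
- **Baseline table.** Section 9.4.5 names PFDI, the pain scale, pain medication and the activity scale, but none of the four.

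For the models, Section 9.4.3 applies the generalized linear mixed model of Section 9.4.2 to the secondary measures. Its covariates are given thus: "Demographics and other characteristics at baseline (treatment group, age, BMI, menopausal status, parity, duration and severity of ODS) will be included", with surgeon as a random effect.

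Section 8.1 also calls for an "Incontinence Severity Index to assess the presence and severity of urinary incontinence specifically".

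**The concern.** A randomized comparison of post-operative scores needs no baseline to be unbiased. A baseline does three other things here. It allows change from before surgery to be described in each arm, which matters because Section 2.1 motivates the trial partly by quality-of-life burden and by quality-of-life improvement in the earlier case series. It shows whether the arms were alike on the instrument at entry, which is not assured with about 48 evaluable women per arm. And, used as a covariate, it removes outcome variance.

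For PFIQ, SF-36, EQ-5D and Brink the gap is in data collection: once a woman has had her operation, her pre-operative score cannot be recovered. For the PFDI subscales, pain and activity the gap is only in the model, because the screening value exists and is not used.

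**Working it through.** **No figure in the plan to reproduce.** Section 9.2 gives power only for the anatomical primary outcome. No standard deviation, correlation, sample size or power is given for any secondary score, so the results below are in standard deviation (SD) units.

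**Where each instrument is measured**

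| Instrument | Before surgery | After surgery | Source |
|---|---|---|---|
| PFIQ, EQ-5D | none | 2, 12, 24 months | 1.3, 3, App. D, App. E |
| SF-36 | none | 2 weeks; 2, 12, 24 months | 1.3, 3, App. D, App. E |
| Brink | none | 2, 12, 24 months | 1.3, 3, 8.1, App. D |
| PFDI | screening | 2, 12, 24 months | 1.3, App. D, App. E |
| Pain, activity | screening | 2 weeks; 2, 12, 24 months | 1.3, App. D, App. E |

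The sections agree with one another, so the missing pre-operative entries are not an artefact of one badly extracted table.

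**Inputs for precision**

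- Evaluable women: 120 × 0.80 = 96, or 48 per arm (Section 9.2).
- Two-sided 5% level (Sections 9.2 and 9.4.1).
- Correlation r between baseline and 24-month score: not in the documents; assumed 0.3, 0.5 or 0.6.

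**Formulas**, for a continuous score, normal approximation, ignoring surgeon clustering:

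- Variance factor with the baseline score as covariate, against no adjustment: 1 − r².
- Standard error of the difference: √(2/48) × √(1 − r²) SD.
- Difference detectable with 80% power: (1.960 + 0.842) × standard error.
- Power for an illustrative 0.5 SD difference: Φ(0.5/SE − 1.960).
- Number per arm that an unadjusted analysis would need for the same precision: 48/(1 − r²).

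| r (assumed) | Variance factor | SE (SD) | Detectable difference (SD) | Power at 0.5 SD | Equivalent n per arm |
|---|---|---|---|---|---|
| no baseline | 1.00 | 0.204 | 0.57 | 69% | 48 |
| 0.3 | 0.91 | 0.195 | 0.55 | 73% | 53 |
| 0.5 | 0.75 | 0.177 | 0.49 | 81% | 64 |
| 0.6 | 0.64 | 0.163 | 0.46 | 86% | 75 |

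The cuts in variance are therefore 9%, 25% and 36%.

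**Allowance for covariates already in the model.** These cuts are measured against a model with no covariates. Suppose, as an illustration, that the listed covariates explain 10% or 20% of outcome variance and that all of this overlaps with the baseline score. At r = 0.5 the further cut is then 1 − 0.75/0.90 = 17% or 1 − 0.75/0.80 = 6%, not 25%.

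**Incontinence severity index.** It is named in Section 8.1. It has no row in Section 1.3, no paragraph in Appendix D and no form title in Appendix E.

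**The case against.** The strongest defence is that nothing promised is impossible. The sentence in Section 4.1 can be read as a list of three items: change in symptoms, quality of life, and incidence of complications. Change cannot govern incidence, so it need not govern quality of life. Section 8.1 only asks for SF-36, EQ-5D and PFIQ scores to be compared, and Section 9.4.3 analyses differences between treatments. Symptom change, the item clearly worded as change, can be computed from PFDI. That reading is fair. A reader might infer that the plan contradicts a stated objective of quality-of-life change; the wording is too ambiguous to support that.

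Some other inferences also go too far:

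- **No within-patient benefit can be shown.** PFDI, pain, activity, bowel habit, POPQ and the compression ratio all have screening values. Women also rate their condition against how it was before surgery, although that is a retrospective rating, which Sections 3 and 8.1 tie to bladder function.
- **Nothing adjusts for baseline differences.** ODS severity and duration, age, BMI, parity and menopausal status are in the model. ODS severity may partly stand in for baseline CRADI, though it is tied to no instrument and is not a baseline SF-36, EQ-5D, PFIQ or Brink score.
- **Appendix E confirms the Brink timing.** It does not mention Brink. That point rests on Sections 1.3, 3 and 8.1 and on Appendix D.
- **The incontinence index can never be analysed.** Appendix E gives form titles, not contents, so the documents show only that no schedule, SOP or form title names it. UDI, with a screening value through PFDI, covers urinary function more generally.

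It is also true that these are secondary measures without a power statement, that no hypothesis in Section 9.1 concerns quality of life or Brink, and that Section 9.4.1 leaves room for detail before database lock. This limits the importance of the point. It does not explain why scores already collected are left out of the models.

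**Conclusion.** The point holds in limited form. On PFIQ, SF-36, EQ-5D and Brink, change from before surgery and baseline balance cannot be assessed; change between post-operative visits can. The secondary models leave out the outcome's own baseline score for every instrument, including those for which it is available.

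The cost is precision, not bias. The 9% to 36% range rests wholly on the assumed correlations of 0.3 to 0.6, applies to continuous scores, and shrinks where the listed covariates carry the same information. It does not carry over to the yes/no OD-symptom endpoint, since OD symptoms are an entry requirement (Section 5.1) and that endpoint has almost no baseline variation. The primary endpoint and the safety analyses are unaffected. The change is worth making because it is cheap and because missing pre-operative scores cannot be recovered later.

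**What to change.** 1. **Section 9.4.3:** state that each continuous secondary outcome is analysed with its own baseline score as a covariate, starting with the PFDI subscales, pain and activity. This needs only wording before database lock, uses data already collected, and also serves women already enrolled.
2. **Sections 1.3 and 3, Appendices D and E:** add PFIQ, SF-36 and EQ-5D at the Initial Appointment. Research consent is scheduled there and randomization comes later, so the rule in Section 10.1.1.2 against study questionnaires before signed consent is respected. The cost is a modest questionnaire burden at an existing visit, and women already operated on will lack these baselines. The plan should say how they enter the adjusted models. Add the three instruments to the list in Section 9.4.5.
3. **Brink:** a baseline is optional. The scheduled pre-operative physical exam is at screening, before research consent, so Brink should be added only if it is recorded after consent and before randomization. That may need an extra exam.
4. **Section 8.1 (minor):** place the incontinence severity index on the schedules and in Appendix D, or delete it. Correct the instrument name under the PFIQ heading in Appendix D at the same time.

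### PFIQ, SF-36, EQ-5D and Brink are never measured before surgery, so pre- to post-operative change in QOL cannot be derived on these scales and the secondary models cannot adjust for each instrument's own baseline

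*Combined protocol and SAP*

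**What the plan says.** Section 4.1 sets the secondary aims: "The secondary objectives include comparing the change in pelvic floor disorder symptoms including OD and fecal incontinence symptoms, QOL". The sentence then goes on to the incidence of complications.

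The measurement times for the four instruments are all post-operative:

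- Section 3 (Outcomes and Measurements), on QOL: "Short Form Health Survey (SF-36) (70), EuroQol-5D (EQ-5D) (71) at 2, 12 and 24 months postoperatively". PFIQ is in the same item. SF-36 is also given to a subset at 2 weeks.
- Section 3, on muscle strength: "Pelvic muscle strength measured by the Brink Scale at 2, 12, and 24 months postoperatively".
- Appendix D (SOP 4), Brink: "Brink assessment will be completed by investigators during 2-month, 12-month, and 24-month post-operative appointments".
- Appendix D, SF-36: "SF-36 assessment will be completed by the research personnel during 2-week, 2-month, 12-month, and 24-month post-operative appointments".
- Appendix D, EQ-5D: "EQ-5D assessment will be completed by the research personnel during 2-month, 12-month, and 24-month post-operative appointments".
- Appendix D, under the PFIQ heading: "PFDI assessment will be completed by research personnel during 2-month, 12-month, and 24-month post-operative appointments". The sentence names PFDI, but the heading and the scoring text that follows are for PFIQ-7.

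The Schedule of Activities (1.3), section 8.1 and the Schedule of Forms (Appendix E, Forms 10 to 12) show no pre-operative administration either. The list of baseline characteristics in 9.4.5 contains none of the four. Section 9.4.3 analyses these measures with the mixed model of 9.4.2, whose covariates are age, BMI, menopausal status, parity, and duration and severity of ODS.

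**The concern.** A change score needs a starting value, and here the earliest value on each scale is already post-operative. If section 4.1 means change in QOL, the trial cannot report it on any of the three QOL instruments it uses.

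The instrument's own baseline is also usually the strongest available predictor of a later score on the same scale. Without it, the treatment comparison is less precise than it could be, and nobody can check whether the arms started level. Section 9.2 projects 20% loss to follow-up and section 9.4.3 rules out imputation for secondary measures. A baseline score would also show whether the women lost differ in starting QOL from those who stay.

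The gap does not look like a general policy. PFDI, the Pain Scale and the Activity Scale all have a screening value.

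**Working it through.** **Step 1. Trace each instrument** through 1.3, 3, 8.1, 9.4.5, Appendix D and Appendix E.

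| Instrument | Before surgery | After surgery | In 9.4.5 baseline list |
|---|---|---|---|
| PFDI | Screening | 2, 12, 24 months | yes |
| Pain Scale, Activity Scale | Screening | 2 weeks; 2, 12, 24 months | yes |
| PFIQ | none | 2, 12, 24 months | no |
| SF-36 | none | 2 weeks; 2, 12, 24 months | no |
| EQ-5D | none | 2, 12, 24 months | no |
| Brink | none | 2, 12, 24 months | no |

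Prose and both schedule tables agree, so this is not a damaged table. Section 4.1 does say that data are collected at baseline, but it names no instrument and so does not fill the gap. Pre- to post-operative change on the last four rows is derivable for 0 of up to 120 women.

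**Step 2. Cost in precision (illustration).** The plan gives no figure to reproduce here. Inputs from the documents are 48 evaluable women per arm (9.2), a two-sided 5% level (9.4.1), and an ICC of 0.01 with 16 women per surgeon (9.2, set for the anatomical endpoint and borrowed here). Assumed inputs are 80% power and a correlation r between the pre-operative and 24-month score of 0.3 to 0.7.

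- Residual variance after adjustment: 1 − r².
- Equivalent sample-size multiple: 1/(1 − r²).
- Detectable difference in SD units: (1.960 + 0.842) × √(2(1 − r²)/48).
- Design effect: 1 + (16 − 1) × 0.01 = 1.15, giving 48/1.15 = 41.7 effective women per arm.

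| Own baseline | 1 − r² | Multiple | Detectable difference, n = 48 | Power at 0.5 SD, n = 48 | Detectable difference, n = 41.7 |
|---|---|---|---|---|---|
| none (as planned) | 1.00 | 1.00 | 0.572 | 69% | 0.613 |
| r = 0.3 | 0.91 | 1.10 | 0.546 | 73% | 0.585 |
| r = 0.5 | 0.75 | 1.33 | 0.495 | 81% | 0.531 |
| r = 0.7 | 0.51 | 1.96 | 0.408 | 93% | 0.438 |

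The variance reductions are 9%, 25% and 51%. The reference row has no covariates at all, whereas the planned model already has several. The relevant gain is what the own baseline explains beyond those, so these figures are upper-end illustrations.

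**Step 3. Where a baseline could be taken.** The Schedule of Activities places research consent at the Initial appointment, after Screening, and section 10.1.1.2 allows no study questionnaires before signed consent. The Initial appointment is therefore the first scheduled visit that fits, and it precedes randomisation. No physical examination is marked there or at any later visit before randomisation, which matters for Brink.

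**The case against.** The section 4.1 sentence need not promise change in QOL. Change cannot sensibly govern the incidence of complications later in the same list, so it may attach to symptoms only, and symptoms have a screening PFDI. Sections 3, 8.1 and 9.4.3 speak of comparing scores or treatment differences, not change in QOL. This stands: the sentence is ambiguous, and a flat contradiction cannot be claimed. On that reading the lost precision and balance check remain.

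A reader might infer that the QOL comparisons are biased or wholly unadjusted. The documents do not support that. Randomisation protects the comparison of post-operative scores, the planned model adjusts for demographics and ODS duration and severity, and screening PFDI, Pain and Activity scores exist. Only the own-instrument baseline is missing.

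A reader might also infer that a promised change in muscle strength is lost. Brink is not in the section 4.1 sentence, and no section promises change in it.

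Nor does any section propose using the first post-operative score as a baseline; that would be an error only if someone did it.

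Finally, some information on change survives. Change between post-operative visits can be derived, and the Impression of Improvement item asks about the condition compared with before surgery, although section 3 frames it as bladder function. Neither replaces a pre-operative QOL score.

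**Conclusion.** The point holds in a limited form. Four secondary measures have no pre-operative value anywhere in the plan. Pre- to post-operative change in QOL, which section 4.1 can be read as naming an objective, cannot be derived on PFIQ, SF-36 or EQ-5D for any woman, and the 9.4.3 models cannot use the own baseline of any of the four.

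The loss is within-woman change, precision and a balance check, not validity. Its size in precision is at most a 9% to 51% variance reduction forgone, resting on an assumed correlation of 0.3 to 0.7, and it shrinks to the extent that the planned covariates predict the scores. The primary endpoint and the secondary endpoint stated in 9.4.3 (presence of OD symptoms at 24 months) are unaffected. The change is worth making but is not essential to the trial's main conclusion.

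**What to change.** - Give PFIQ-7, SF-36 and EQ-5D (Forms 10 to 12) at the Initial appointment, after research consent and before randomisation. Screening is unsuitable because it precedes consent. Section 6.3 says participants cannot be masked, so a score given after allocation would not be a clean baseline.
- Update 1.3, section 3, 8.1, 9.4.5, Appendix D (SOP 4) and Appendix E, and correct the instrument name in the PFIQ paragraph of SOP 4.
- Add each instrument's baseline score as a covariate in its 9.4.3 model.
- For women already treated, use a missing-baseline indicator or mean imputation of the covariate. Do not use a post-operative score as baseline.
- Add a baseline Brink only if it can be done at an existing examination after consent and before randomisation; the schedule currently marks none.
- If baselines are not collected, reword section 4.1 so that QOL is compared as post-operative scores.

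The cost is about 60 extra responses per woman (36 for SF-36, 7 × 3 = 21 for PFIQ-7 and 5 for EQ-5D, 62 in all) and a short amendment. Women already treated will still have no baseline.
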